Document:

Study protocol and statistical analysis plan

Protocol:

EFFECT OF A NUTRITIONAL SUPPORT SYSTEM (DIET, SUPPLEMENTS AND PROBIOTIC) FOR IMPROVING GROSS MOTOR FUNCTION IN CEREBRAL PALSY. AN EXPLORATORY RANDOMIZED CONTROLLED CLINICAL TRIAL

NCT number:

2014/03001

Date:

March 28, 2014

EFFECT OF A NUTRITIONAL SUPPORT SYSTEM (DIET, SUPPLEMENTS AND PROBIOTIC) FOR IMPROVING GROSS MOTOR FUNCTION IN CEREBRAL PALSY. AN EXPLORATORY RANDOMIZED CONTROLLED CLINICAL TRIAL

Abstract

Background: Most patients with cerebral palsy (CP) are dependent on parents due to the spasticity and limitations in their gross motor function. Additionally, many of them do not respond to physical therapy due to deterioration in their nutritional status, which is secondary to gastrointestinal disorders, parasitosis, dysbiosis and the catabolic state of the disease itself. Evidence suggests that greater independence and better clinical response can be achieved by correcting the nutritional status. However, basic treatments only contemplate the calculation of energy requirements and do not consider important nutrients in particular, supplementation with glutamine, arginine, zinc, selenium, colexicaliferol, nicotinic acid, spirulina, omega 3, ascorbic acid, vegetal protein or even probiotics.

Objective: To determine the effect of using a nutritional support system (NSS) diet, supplements and probiotic on the gross motor function in children with CP with spastic diparesic and Gross Motor Function Classification System III (GMFCS III).

Material and methods: In an exploratory study with controlled clinical trial design, 30 patients were randomly assigned to receive: 1) dietary surveillance and conventional therapy (FG), 2) deworming and WHO diet (CG), or 3) deworming and the NSS (IG). The patients were recruited from the CRIT Tlalnepantla Estado de México. Males and females aged 4-12 years were included with CP and spastic diparesic GMFCS III, and who had a full-time caregiver and whose parents agreed to participate. They were studied for thirteen weeks. Gross motor function was evaluated at baseline and at 7 and 13 weeks after therapy using the GMFM scale.

Results: The IG-treated group presented a significant improvement in standing and walking parameters analyzed in the GMFM compared with FG and CG groups. Fifty percent of the IG-treated patients managed to walk, while in the other groups no patients were able to walk.

Conclusion: The NSS used in the present work, improves gross motor function and promotes walking in patients with CP.

1. Introduction

Cerebral palsy (CP) is the most common physical disability in childhood. The prevalence worldwide and in developed countries is approximate to 2-2.5 cases per 1,000 live births [1-2]. According to the Center for Disease Control (CDC) the cost per person was estimated at around 921,000 dollars per year in the United States (2003), while the costs for general medical assistance amounted to 11,500 million dollars [3]. CP is a permanent movement disorder characterized by a persistent postural tone, causing limitation of activity. This is attributed to non-progressive damage on a developing and immature brain that is originated in the fetal, perinatal period (greater percentage) or first years of life. CP is accompanied by alterations in sensation, cognition, communication, perception, spasticity, seizures, disorders in swallowing and malnutrition [4].

An important aspect affecting evolution and functional independence in CP is spasticity which is a reflection of the damage in the Pyramidal System (PS). Traditional treatment for CP-patients, generates a recovery of 2% [5] per year and is based on rehabilitation, botulinum toxin therapy, general care and in the case of malnutrition or disorders in swallowing, nutritional support which is based on the adaptation of Krick to the Schofield formula [6].

In spite of these approaches, CP continues to be the aim of numerous investigations, especially to find new therapeutic strategies.

Currently, the use of functional foods, supplements or even the administration of probiotics or prebiotics as a therapeutic strategy has become a very important research area.

In line with this, several investigations have shown that a number of nutrients are endowed with therapeutic properties including the protection and repair of the central nervous system (CNS). Arginine, for instance, participates in the formation of Nitric Oxide (NO) which is associated with neuronal regeneration and protection of the CNS [7]. Docosahexaenoic acid (DHA) and sphingosine 1 phosphate (S1P) prevent the early death of newly generated neurons [8]. Omega 3 polyunsaturated fatty acids (PUFAs n-3) participate in brain plasticity, neurogenesis, memory and brain repair. Neuromuscular alterations after cerebral ischaemia, improve after omega-3 treatment [9-10].

On the other hand, supplementation with probiotics have also been proposed as a therapeutic strategy for alleviating CNS pathologies [11]. In this case, probiotics have been used to stimulate the production of neurotransmitters, memory, neuroregeneration and also for correcting malabsorption [12].

In order to provide CP-patients with the best therapeutic strategy, it is also important to consider the use of several metabolic rescue pathways to produce energy, including lactate and alanine cycles, where glutamine and glutamic acid are the main substrates [13]. Additionally, deficiencies have also been reported in plasma concentrations of iron, folate, niacin, calcium, vitamin D and E, zinc and selenium even in children with CP who were being supplemented [14-15-16].

Finally, it is relevant to take into account that, 3,500 million people in the world are parasitized and of them, mainly are children, increasing the risk of malnutrition in this group of people [17]. This concomitant factor, makes malnutrition, an even more important problem in CP patients.

It can be said, therefore, that there are several factors that need to be addressed in order to establish the best therapeutic strategy for CP. That is why; in the present study, we tested

an integral food system that includes nutrition, metabolic support, deworming and neurological remodeling support.

2. Materials and methods

The exploratory study was designed as a controlled clinical trial which was randomized and blind, whereby sampling was achieved using the design of consecutive cases. CP-patients with spastic diparesis and GMFCS III were enrolled in this study and treated at the Children's Telethon Rehabilitation Center (CRIT) in Tlalnepantla Estado de México. The duration of the study was 13 weeks for each participant.

The trial complied with the principles of the Declaration of Helsinki and the Mexican norm NOM-012-SSA3-2012 for scientific research in humans. This clinical trial was approved by the Committee of Research of the Faculty of Health Sciences of the Universidad Anáhuac México Campus Norte with the number 2014/03001. The parent or guardian and the patient (in the event that they could sign) signed the informed consent letter voluntarily.

2.1 Participants

Fifty-three children were interviewed. Thirty met the inclusion criteria (see figure 1).

Inclusion criteria: CP-patients with spastic diparesis and GMFCS III (these patients demonstrate elevated functionality in the categories of lying/rolling, sitting and crawling), of both genders aged between 4 and 12 years old, who had support from a full-time caregiver, and who were able to feed orally.

Non-inclusion criteria: CP-patients presenting another catabolic disease which could increase the risk of malnutrition (renal, cardiovascular, pulmonary, hepatic or immunological disease), those presenting infections or receiving antibiotic treatment at least 15 days before starting the study. Patients who had received therapy with botulinum toxin or muscle

relaxants in the last 6 months. CP-patients presenting severe gastroesophageal reflux or with any type of surgery performed in the last 9 months and, patients walking by themselves.

[figure not shown]

Fig. 1. CONSORT flow diagram.

2.2 Group Assignments

The thirty eligible patients were randomly assigned through a sequence of numbers. These were then divided into three groups: 1) Follow-up group (FG, n=10), only their usual diet was monitored; 2) Conventional Group (CG, n=10), were deworming and received the nutritional therapy recommended by the WHO; 3) Intervention Group (IG, n=10), were deworming and received the NSS which consists of a shake based diet with functional ingredients, high levels of vegetables, fruits, cereals, root-vegetables and fish as well as supplementation with glutamine, arginine, folic acid, nicotinic acid, zinc, selenium, cholecalciferol, ascorbic acid, spirulina, protein vegetable, PUFAs n-3 and probiotics (*Saccharomyces Boulardii* (200 mg every 12 hours for 3 days in the basal period and at week 7). All participants received Bobath physical therapy.

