2.3 Procedures

Once the participants were selected, parents and CP-patients were called to explain the protocol and to collect their informed consent forms. Upon entering the study, the nutritional history and GMFM scale qualification was obtained and recorded from each patient. Thereafter CP-patients were randomly allocated into 3 groups (FG, CG and IG). The energy calculation for the CG and IG groups was performed with the Krick formula (50% carbohydrates, 30% lipids, and 20% proteins).

The parents and / or caregivers of the participants were trained on the project, procedures, as well as feeding and supplementation schemes if required. At the beginning of the treatment, the CG and IG groups were dewormed with nitazoxanide at a dosage of 7.5 mg / kg every 12 hours for 3 days.

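### Baseline GMFM is recorded before allocation but is used neither in the described 10/10/10 assignment nor in the between-group tests, which costs precision in a 30-child trial

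*Combined protocol and SAP*

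**What the plan says.** Allocation is described in two places. Section 2.2 says "The thirty eligible patients were randomly assigned through a sequence of numbers. These were then divided into three groups" and lists the three arms: "Follow-up group (FG, n=10), only their usual diet was monitored"; "Conventional Group (CG, n=10"); and "Intervention Group (IG, n=10"). Section 2.3 first describes consent, then the nutritional history and GMFM score recorded at entry, and continues: "Thereafter CP-patients were randomly allocated into 3 groups (FG, CG and IG").

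Section 2.1 admits children with spastic diparesis at GMFCS III, "of both genders aged between 4 and 12 years old", and excludes those already walking by themselves. Section 2 describes recruitment as one "whereby sampling was achieved using the design of consecutive cases".

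Section 2.7 names one-way ANOVA for normal data and Kruskal-Wallis otherwise, with repeated-measures ANOVA for differences within a group. It names no baseline covariate and does not say whether the between-group tests use the final score or the change from baseline.

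No section mentions stratification, blocking, matching, who produced or held the sequence, or whether the 30 were allocated together. The numbered envelopes in section 2.4 hold supplements and have no role in allocation.

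**The concern.** When a score that is likely to predict the outcome is known for each child before allocation, it can be used to balance the arms, to adjust the comparison, or both. The plan describes neither. With 10 children per arm, chance alone can leave one arm clearly ahead on standing and walking at the start.

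Two results are exposed. For the GMFM scores, an unadjusted comparison carries all of the between-child variation that baseline could explain. For the walking result in the abstract (half of the intervention group, none elsewhere), five events leave little room for regression adjustment. One child who started close to walking can decide a pairwise test.

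**Working it through.** **The plan's own figure.** There is no power, sample-size or imbalance calculation to reproduce. The only check is 3 × 10 = 30, which agrees.

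**Inputs.** From the documents: 10 per arm, three arms (2.2); GMFM before allocation (2.3); significance level 0.05 (2.7). Assumed: a normally distributed baseline score, a two-sided test, and a baseline-to-final correlation ρ between 0.5 and 0.95. The documents give no SD or correlation.

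**Chance imbalance, one pair of arms.** The SD of the standardised difference in baseline means is √(1/10 + 1/10) = 0.447, so its 95% range is ±1.96 × 0.447 = ±0.88 SD.
- P(difference > 0.5 SD) = 2[1 − Φ(0.5/0.447)] = 26%.
- P(difference > 0.8 SD) = 2[1 − Φ(0.8/0.447)] = 7%.

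**Three arms, by simulation (100,000 draws).**

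| Assignment | SD of pairwise difference | One pair > 0.5 SD | Any pair > 0.5 SD | Any pair > 0.8 SD |
|---|---|---|---|---|
| Unstratified 10/10/10 | 0.447 | 26% | 50% | 17% |
| Two strata cut at the median, 5/5/5 in each | 0.27 | 7% | 16% | 1% |
| Ten ranked triplets | 0.10 | about 0 | about 0 | about 0 |

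The 7% needs a cut at the median. With a fixed cut and permuted blocks it is 7–9% if the cut falls at the median, 10–11% if it lies 0.5 SD above, and 16–17% if it lies 1 SD above.

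**What an imbalance does to an unadjusted test of the final score.** Given a baseline difference D and no treatment effect, the final difference has mean ρD and SD √(1 − ρ²) × 0.447. The test rejects beyond 1.96 × 0.447 = 0.877.
- D = 0.8 and ρ = 0.8: mean 0.64, SD 0.6 × 0.447 = 0.268, rejection rate 19%. Over ρ from 0.5 to 0.95 the range is 11% to 21%.
- D = 0.5: 0.2% to 5.5% over the same range, so there is no material inflation.
- Averaged over all draws, the rate stays at 5%.

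**Precision.** Adjusting for continuous baseline leaves a residual variance of 1 − ρ²: 0.51, 0.36 and 0.19 of the unadjusted variance for ρ = 0.7, 0.8 and 0.9. In simulation with ρ = 0.8 and a true effect of 0.8 SD (both assumed), pairwise power is about 39% unadjusted, 57% with a median-split stratum term, and 81% with continuous baseline.

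**Walking result (Fisher's exact test, two arms).** 5/10 against 0/10 gives p = 0.033. With one fewer walker in the intervention group, 4/10 against 0/10 gives p = 0.087. With one walker in the comparator, 5/10 against 1/10 gives p = 0.14.

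**The case against.** The strongest reply is that chance imbalance under valid randomisation is not bias. The type I error averages 5%, and at 0.5 SD even the conditional rate is not materially raised. Not stratifying 30 children in a trial labelled exploratory is a defensible choice. Entry is already confined to one centre, one form of cerebral palsy, GMFCS III and children not yet walking alone. All of this stands, so the point is about precision and interpretability. The entry limits do not remove the spread in standing and walking scores, however, and the figures above are in units of whatever SD remains.

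It can also be said that baseline enters the repeated-measures ANOVA. Section 2.7 confines that analysis to differences within a group. If the one-way ANOVA were run on change scores, part of the gain would already be taken: at ρ = 0.8 the variance of change is 2(1 − 0.8) = 0.40 of the unadjusted variance, against 0.36 with adjustment. The plan does not say so, and at ρ = 0.5 change gives no gain, since 2(1 − 0.5) = 1.

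A reader might infer something stronger: that a plain, unconcealed list let staff foresee the next arm. The documents do not support this.
- They are silent on concealment, and silence does not show that there was none.
- Independent draws give exactly 10/10/10 only 30!/(10!³ × 3³⁰) = 2.7% of the time, so some undescribed restriction was probably used. Blocking or stratification cannot be excluded, and the 26% and 50% apply only if there was no stratification.
- Guessing the fullest remaining arm is right 13.7 times in 30, against 10 by chance, only if children were allocated one by one and the recruiter knew the quotas and every past assignment. The wording of section 2.2 fits a single draw of all 30 equally well, and consecutive cases describes the sampling.

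**Conclusion.** The point holds as a cheap improvement. As described, neither the assignment nor the between-group tests use the baseline GMFM. If the draw was unstratified and the score roughly normal, there is about a 26% chance that the intervention and conventional groups differ by more than 0.5 SD, and about a 50% chance that some pair does. The larger loss is in precision: with ρ = 0.8 assumed, baseline adjustment removes 64% of the variance (1 − 0.36). The pairwise walking result turns on a single child. Pooling both comparators (5/10 against 0/20) would be less fragile, but the plan does not provide for it. None of this shows a biased test or foreseeable allocation.

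**What to change.** **Design, where allocation is still open.** Randomise within two strata of baseline standing plus walking GMFM, cut near the median, or within ranked triplets if all 30 are scored before the draw. Use small blocks only with a concealed list. If past assignments are known, best guesses are right 18.3 times in 30 with blocks of 3 and 16.8 with blocks of 6.

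**Analysis, in either case.** Compare arms with a model of the final GMFM score that includes continuous baseline GMFM and any stratum used. The abstract already reports results, so for this trial the adjusted comparison is probably the only part still available. For walking, show the baseline standing and walking scores by arm and describe the result as fragile. Exact stratified or penalised methods exist for sparse outcomes but would have low power.

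**Reporting.** State how the sequence was generated and restricted, who held it, how it was concealed, and whether the 30 were allocated together or one by one.

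**Cost.** One or two degrees of freedom, slightly more randomisation work, and a few sentences of text. No added patients or visits.

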2.3 Procedures

Once the participants were selected, parents and CP-patients were called to explain the protocol and to collect their informed consent forms. Upon entering the study, the nutritional history and GMFM scale qualification was obtained and recorded from each patient. Thereafter CP-patients were randomly allocated into 3 groups (FG, CG and IG). The energy calculation for the CG and IG groups was performed with the Krick formula (50% carbohydrates, 30% lipids, and 20% proteins).

The parents and / or caregivers of the participants were trained on the project, procedures, as well as feeding and supplementation schemes if required. At the beginning of the treatment, the CG and IG groups were dewormed with nitazoxanide at a dosage of 7.5 mg / kg every 12 hours for 3 days.

2.4 Shakes and Supplementation

The IG supplements were mixed in numbered envelopes and administered in three shakes: shakes 1 and 3 contained amaranth, oats, avocado, banana, egg white, cinnamon and almond milk. Shake 1 was to be taken in the morning and shake 3 in the evening. Shake 2 contained celery, orange, pineapple, nopal, radish and ginger and was to be drunk in the morning together with shake 1.

The ingredients and administration of the envelopes were as follows: **Envelope 1** contained 4.9g of Spirulina Maximum, 100mg ascorbic acid, 5mg folic acid and 10mg of glutamine. This envelope was to be added to shake 1 during the first 10 days of the intervention. **Envelope 2** contained 1g PUFAs n-3 and was to be added to shake 2 which was given throughout the intervention. **Envelope 3** contained 4.9g of Spirulina Maximum, 100mg ascorbic acid, 5mg folic acid, 5.2g vegetable protein, 125mg nicotinic acid, 50mg zinc, 100 mcg selenium and 800 UI cholecalciferol. This envelope was to be added to shake 1 from day 11 until the end of week 6, after which it was suspended for 10 days and substituted for

envelope 5 and then to be retaken until the end of the intervention. **Envelope 4** contained 1g arginine and was to be added to shake 3 from day 8 until the end of the intervention. **Envelope 5** contained the same ingredients as envelope 3 with an additional 10mg glutamine and was to be added to shake 1 from the start of week 7 for 10 days, after which envelope 3 was restarted.

2.5 Follow up

The participants attended CRIT twice a week to receive physical therapy and once a week for a clinical and nutritional checkup where they would hand in their food diaries and their supplement envelopes to be counted to evaluate their adherence to the course of treatment. On days when the patients attended physical therapy, they were supervised to ensure that they had breakfast, mid-morning snack and lunch.

2.6 GMFM assessment

The GMFM scale was performed at baseline time and weeks 7 and 13 after intervention. It was applied by CRIT staff. The evaluators were the blind aspect of the study as they did not have access to any information about the treatment each child was receiving.

This scale assesses five general parameters: 1. Lying (decubitus) and rolling over (GMFAV), 2. Sitting (GMFB), 3. Crawling and kneeling (GMFC), 4. Standing (GMFD), 5. Walking (GMFE) and one final total item (GMFF). The scoring system consists of 88 items and each one is valued based on the following criteria: 0= No, 1= start, 2= Partially Complete, 3= Complete, NE= Not evaluated [18-19].

2.7 Statistical methods

In order to know the type of distribution of the data, the tests of Kolmogorov-Smirnov, D'Agostino-Pearson and Shapiro-Wilk were applied. Analysis of data was performed using

the continuous variables mean and standard deviation were used if the distribution was normal, and if it didn't present normal distribution the median and range were used. Percentages and proportions assessed the ordinal variables. Analysis of data with normal distributions was performed using One-way ANOVA. ANOVA of repeated measurements was used to analyze the intragroup difference. When the distribution did not show normality, Kruskal Wallis test followed by the Dunn post hoc test. and Tukey were applied respectively to post hoc tests. The level of significance was <0.05 in all cases.

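### Section 2.7 lets three normality tests choose between ANOVA and Kruskal-Wallis without saying which governs, so where they disagree the analysis cannot be determined from the plan

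*Combined protocol and SAP*

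**What the plan says.** Section 2.7 first establishes the type of distribution: "the tests of Kolmogorov-Smirnov, D'Agostino-Pearson and Shapiro-Wilk were applied". The answer selects the summary statistics (mean and standard deviation, or median and range) and the between-group test. On one side, "Analysis of data with normal distributions was performed using One-way ANOVA". On the other, "When the distribution did not show normality, Kruskal Wallis test followed by the Dunn post hoc test". Within groups, "ANOVA of repeated measurements was used to analyze the intragroup difference", and no non-parametric counterpart is clearly named. The only threshold given is general: "The level of significance was <0.05 in all cases".

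Section 2.2 puts 10 children in each of three arms. Section 2.6 lists six GMFM scores (five dimensions and a total), assessed at baseline, week 7 and week 13. It names no primary score or visit. Section 2.1 describes the population: "these patients demonstrate elevated functionality in the categories of lying/rolling, sitting and crawling". It also excludes children who walk by themselves.

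**The concern.** A rule that lets the data choose the test can be followed only if it gives one answer for each data set. Three normality tests of different sensitivity can give different answers on the same small sample, and the plan does not rank or combine them. It also leaves open the unit tested (each arm, the pooled values or the residuals), the quantity (raw score or change) and the visit.

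As a result, two analysts following Section 2.7 in good faith could report different tests and different summaries for the same score, and one score could be analysed by means at week 7 and by ranks at week 13. The abstract reports significant improvement in standing and walking, but Section 2.7 does not let a reader work out which test lies behind either claim.

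There is also a question of efficiency. As named, one-way ANOVA and Kruskal-Wallis have no place for the baseline GMFM score, although Sections 2.3 and 2.6 show that it is collected for every child.

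**Working it through.** The plan gives no sample-size, power or error-rate figure, so there is nothing to reproduce. The check is by simulation.

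**Inputs from the documents.** Three arms of 10 (Section 2.2), three normality tests and a 0.05 level (Section 2.7), six scores at three times (Section 2.6). The gate is therefore met 6 × 3 = 18 times. That is 18 × 3 = 54 normality tests on pooled data, or 54 × 3 = 162 if each arm is tested.

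**Assumptions.** The documents give no score distribution. The main shapes were:
- normal;
- floor: max(0, N(5, 12)), which puts Φ(−5/12) = 34% of values at the floor;
- ceiling: min(100, N(95, 8)), which puts 1 − Φ(5/8) = 27% at the ceiling;
- lognormal with sigma 0.8.

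Kolmogorov-Smirnov was run with estimated parameters (Lilliefors). For the per-arm reading, a test calls a score non-normal if it rejects in any arm. The tests conflict when at least one, but not all three, call it non-normal.

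**Step 1: how often the branch is undetermined.**

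| Shape | Per arm (n = 10) | Pooled residuals (n = 30) |
|---|---|---|
| Normal | 24% | 10% |
| Floor | 50% | 54% |
| Ceiling | 55% | 53% |

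The lognormal shape gave 27% per arm. A second simulation with other shapes (chi-square with 4 df, lognormal with sigma 0.5, exponential, 30% floor) gave 36-54% per arm, and 22% for normal data. The version of Kolmogorov-Smirnov matters. The uncorrected table almost never rejects at n = 10, and using it raised per-arm conflict to 89% for the floor shape and 77% for the ceiling shape. The plan does not say which version applies.

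**Step 2: effect on type I error.** With no treatment effect and one fixed test, the error rate stayed near nominal: 4.0-4.7% in the second simulation and 4.7-5.4% in a run of the main shapes. If the analyst may take the smaller p-value whenever the normality tests conflict, it was 5.1-5.7% in the second simulation, 4.1-5.5% in one run of the main shapes, and 5.8% (floor) and 6.1% (ceiling) in another of 3,000 trials. Monte Carlo error at that size is √(0.05 × 0.95 / 3000) = 0.4 percentage points. Conflict together with opposite verdicts from ANOVA and Kruskal-Wallis at 0.05 occurred in only 0.6-1.3% of null trials.

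**Step 3: when there is an effect.** With one arm shifted by an assumed 1.2 SD, ANOVA and Kruskal-Wallis fell on opposite sides of 0.05 in 7-13% of trials. This counts all trials, not only those where the normality tests conflict.

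**Step 4: what ignoring baseline costs.** Assume one arm shifted by 1 SD. The noncentrality for one-way ANOVA on the follow-up score is 10 × (2/3) = 6.67, which on F(2, 27) gives 58% power. Adjusting for a baseline with correlation r divides the noncentrality by 1 − r²: 6.67/0.75 = 8.89 at r = 0.5, 6.67/0.51 = 13.07 at r = 0.7, and 6.67/0.19 = 35.1 at r = 0.9. Simulated power for the adjusted model was 69%, 84% and over 99%.

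These gains are measured against an analysis of the follow-up score alone. If change scores were meant, their variance relative to the raw score is 2(1 − r) = 1.0, 0.6 and 0.2, against 0.75, 0.51 and 0.19 after adjustment. The adjusted model is still the more precise, but by little at high correlation.

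**The case against.** The strongest reply is that the harm is small. A reader might infer that the stated 0.05 level is not the real error rate. The simulations do not support that as a serious charge, because even a free choice at every conflict leaves the error rate at or below about 6% per score. The lack of any adjustment across six scores matters far more (1 − 0.95⁶ = 26.5% if they were independent), but that is a separate point. The trial also calls itself exploratory. All of this stands, and it makes the point one of reproducibility.

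Three other stronger readings are tempting.
- **That the test for every score is open.** Where all three normality tests agree on a settled unit, Section 2.7 fixes the branch.
- **That the tests are run on arms of 10.** The section does not state the unit. On pooled residuals, conflict falls to about 10% for normal data but stays above 50% for floor and ceiling shapes, so the gap does not depend on this reading.
- **That the plan puts the scores at the ends of the scale.** Section 2.1 says function is elevated in three categories and excludes independent walkers. Ceiling and floor effects are therefore plausible, but the documents give no distribution and the simulated proportions are assumptions.

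A one-line rule naming the governing test and its unit, or Kruskal-Wallis throughout, would also remove the indeterminacy. That is true, but neither would use the baseline score. Finally, one sentence in Section 2.7 breaks off, possibly in text extraction. Nothing here relies on it, since the three tests and both branches stand in intact text.

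**Conclusion.** The point holds as one of pre-specification. Section 2.7 does not determine the between-group analysis when its normality tests disagree, and nothing elsewhere in the document fills the gap. Under the assumed shapes, and with the corrected Kolmogorov-Smirnov test, disagreement arises in roughly 10-24% of comparisons for normal data and 50-55% for floor or ceiling data, depending on the unit tested. The uncorrected version gives higher figures for the floor and ceiling shapes.

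The consequence for type I error is minor. The larger losses are that the analysis cannot be reproduced from the plan, that summaries may not be comparable across scores, and that the baseline measurement is left out of both named between-group tests. A reader might go further and infer that the abstract's findings are a product of test choice. The documents do not support that, because they do not show which test was used or how the normality tests came out.

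**What to change.** Replace the normality gate with one stated analysis for every GMFM score:
- a linear model of the week-13 score on arm and that score's baseline value, reporting arm differences with 95% CIs and a p-value from permuting arm labels;
- the same model for week 7;
- pairwise arm comparisons taken from this model, in place of the separate post hoc procedures;
- Kruskal-Wallis on change from baseline as the only sensitivity analysis;
- within-group repeated-measures results kept as descriptive;
- residual plots shown as description, never used to select a test.

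The cost is one rewritten paragraph and a re-run on data already collected. The analyst loses the freedom to switch tests, and the linear model is only approximate for scores near a floor or ceiling. The permutation p-value does not need normality, but the confidence intervals remain model-based. Since the abstract already reports results, the re-analysis must be labelled post hoc and shown beside the reported analysis.
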